New/enlarging T2 lesions after week 8	included with evidence of disease activity	excluded

Analysis of binary NEDA

The proportions of patients with:

- NEDA
- Treatment discontinuation due to lack of efficacy or death without events prior the withdrawal
- Relapses
- No Relapse
- 24-weeks CDP
- No 24 weeks CDP
- T1 Gd-enhanced lesions after week 8
- No T1 Gd-enhanced lesions after week 8
- New/enlarging T2 lesions after week 8
- No New/enlarging T2 lesions after week 8
- MRI activity (T1 Gd-enhanced lesions or new/enlarging T2 lesions)
- No MRI activity
- Relapses or MRI activity
- 24-weeks CDP or MRI activity
- Clinical activity (Relapses or 24-weeks CDP)
- No clinical activity
- Relapses and MRI activity
- 24-weeks CDP and MRI activity
- Relapses and 24-weeks CDP

post-baseline up to the Week 96 visit will be calculated and presented with a two-sided 95% Clopper-Pearson exact confidence interval.

Protocol-Defined Relapse definition

A protocol-defined MS relapse is an occurrence of new or worsening neurological symptoms attributable to MS that meets the following criteria:

- Symptoms must persist for >24 hours and should not be attributable to confounding clinical factors (e.g., fever, infection, injury, adverse reactions to medications)
- Symptoms should be preceded by neurological stability for at least 30 days
- Symptoms should be accompanied by new objective neurological worsening determined with a timely EDSS/ Functional Systems Score (FSS) assessment, consistent with an increase of at least:
 - ≥ 0.5 points on EDSS scale
 - or ≥ 2 points on one of the following FSS scales: pyramidal, ambulation, cerebellar, brainstem, sensory, or visual
 - or ≥ 1 point on two or more of the following FSS scales: pyramidal, ambulation, cerebellar, brainstem, sensory, or visual

Information related to a PDR will be captured on a clinical relapse event case report form (CRF) page (Multiple Sclerosis Relapse). If the following criteria are satisfied, the clinical relapse will qualify as a PDR:

1. Clinical relapse is reported on eCRF.
2. Check-box of “Did symptoms persist for >24 hours and were not being attributable...” on the Clinical MS relapse event is checked.

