3. Check if the first EDSS assessment at a visit (unscheduled or scheduled) on or after the onset date of the relapse is increased by ≥ 0.5 steps from the previous EDSS; or selected FSS domains relevant to the relapse event (pyramidal, ambulation, cerebellar, brainstem, sensory, or converted visual) are increased by ≥ 2 points on one domain or ≥ 1 point on two or more domains. When deriving this step do the following:
 - Take the last EDSS/FSS score before each clinical relapse onset date
 - Take the first EDSS/FSS score on or after each clinical relapse onset date
 - Calculate the difference between the two scores
 - Select clinical relapses where there is an increase of ≥ 0.5 in EDSS or ≥ 2 on one appropriate FSS domain or ≥ 1 on two or more appropriate FSS domains
4. For each relapse that satisfies the 3 criteria above, check if the following relapses are within 30 days (i.e., the onset dates are ≤ 30 days apart). If they are within 30 days, then the later relapses are not PDR.

24-Week Confirmed Disability Progression (CDP) definition

Disability Progression as measured by EDSS is defined a ≥ 1 -point increase in EDSS score from a baseline EDSS score of 0.0–5.5 inclusive, and a 0.5-increase from a baseline EDSS score higher than 5.5. Because of the variability of EDSS, a single measurement at the baseline visit might not provide a sufficiently reliable baseline EDSS. Therefore, using an average score from two separate measurements may improve the reliability of baseline EDSS and the reliability of confirmed disability progression seen in the study. In the analysis of CDP, baseline EDSS is defined as the average of the EDSS scores at the screening and baseline visits (of note, any baseline visits occurring after the first dosing date will be disregarded in the computation of the baseline EDSS score), without rounding. If one of the EDSS scores from the screening or baseline visit was missing, the other was used for baseline EDSS.

Initial progression can happen at any scheduled or unscheduled visit during the 96-week treatment period.

An initial disability progression becomes confirmed if the following conditions are met:

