4.4.3.5 MRI and clinical outcomes at 6 months and 1 year

MRI data including total number of Gd-enhanced lesions up to Weeks 24 (*i.e. 6-months*) and 48 (*i.e. 1-year*), changes in total T2 lesion volume at Weeks 48 and changes in total T1 hypointense volume at Week 48 have been described as secondary efficacy endpoints.

Total number of new and/or enlarging T2 hyperintense lesions up to Weeks 24 and 48 will be summarized similarly to total number of T1 Gd-enhanced lesions (see section [4.4.2.10](#)).

4.4.3.6 Severity of relapses (hospitalization for MS relapse, use of corticosteroids, residual disability)

Severity of protocol defined relapses including hospitalization longer than 5 days (yes/no), use of corticosteroid (yes/no) and residual disability (yes/no) will be summarized at baseline, weeks 24, 48 and 96 using frequency tables (number and percentage with total number of relapses as denominator).

For protocol defined relapses, a descriptive analysis of the EDSS change between before and after relapse will be performed. This change in EDSS (referred as Chg-EDSS_(after-before)) will be defined as difference between EDSS collected at the last scheduled EDSS measurement available prior to relapse and the EDSS collected at the first scheduled or unscheduled EDSS measurement on or after relapse. Descriptive summary of Chg-EDSS_(after-before) will be presented along with the number of patients by EDSS change categories (≤ 0.5 , 0.5-1.0, 1.0-2.0 and >2.0).

To investigate the evolution of EDSS after relapse, the change between the first EDSS measurement after the relapse and the next scheduled EDSS measurement will be summarized as above. This will be repeated for the change between the first EDSS measurement after the relapse and the second next scheduled EDSS measurement.

To investigate the duration of post relapse residual disability, the number and proportion of patients with an $EDSS_{\text{after relapse} < 24; 48 > \text{weeks}} > EDSS_{\text{before relapse}} + 0.5 * \text{Chg-EDSS}_{(\text{after-before})}$ will be provided. This is illustrated in an example below:

$EDSS_{\text{before relapse}}$	$EDSS_{\text{after relapse}}$	$\text{Chg-EDSS}_{(\text{after-before})}$	$EDSS_{\text{after relapse} < 24 ; 48 > \text{weeks}}$	retained at least 50% of $\text{Chg-EDSS}_{(\text{after-before})}$
3	4	1	4.5	Yes
3	4	1	3.5	No

4.4.3.7 Proportion of patients who have NEDA, as per protocol defined events during a 96-week period and starting from baseline

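### The SAP's post-relapse residual-disability rule excludes exact half retention while its label includes it, and it has no condition that EDSS rose at the relapse.

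*SAP*

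**What the plan says.** SAP Section 4.4.3.6 (severity of relapses) applies to protocol-defined relapses. It defines Chg-EDSS as the first EDSS from relapse onset onward minus the "last scheduled EDSS measurement available prior to relapse". It then sets out the measure at issue: "To investigate the duration of post relapse residual disability, the number and proportion of patients with an" EDSS at 24 or 48 weeks strictly greater than the pre-relapse EDSS plus 0.5 times Chg-EDSS.

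The SAP adds "This is illustrated in an example below" and gives two rows, both with EDSS 3 before and 4 after the relapse, so a change of 1. A later EDSS of 4.5 is scored Yes and a later EDSS of 3.5 is scored No. The column holding these answers is headed "retained at least 50% of" the change.

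SAP Section 4.4.1 fixes which relapses enter. An EDSS rise of 0.5 is one route; another is "≥ 2 points on one of the following FSS scales", and a third is a 1-point rise on two or more scales. The derivation step repeats this: "Select clinical relapses where there is an increase of ≥ 0.5 in EDSS or ≥ 2 on one appropriate FSS domain", with the two-domain route following. Section 4.4.3.6 does not require Chg-EDSS to be positive, and its lowest change category (0.5 or less) has no lower bound.

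**The concern.** Two things look wrong. First, a measure described as keeping at least half of the rise should count a patient who keeps exactly half, and the SAP's own second row does not. A programmer working from the formula and a reader working from the column heading would classify that patient differently.

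Second, the rule presumes a rise to retain. If EDSS did not move at the relapse, the threshold collapses to the pre-relapse EDSS, and the wording about retaining half of the change has no meaning.

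At stake is the interpretation of one reported count and proportion. Post-relapse residual disability is part of a named exploratory endpoint in both documents.

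**Working it through.** **Inputs.** The rule and the example come from SAP 4.4.3.6, and relapse qualification from SAP 4.4.1. The EDSS step size comes from Protocol 4.5.6 (half points), and the meaning of the EDSS levels from Protocol Appendix 3.

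**Rule.** Threshold T = before + 0.5 × Chg-EDSS. The SAP scores Yes if later > T; the label read literally scores Yes if later ≥ T. The percentage retained is 100 × (later − before) / Chg-EDSS.

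**Reproducing the SAP's example.** In both rows T = 3 + 0.5 × 1 = 3.5.

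| Later EDSS | Retained | Formula (>) | Label (≥) | SAP prints |
|---|---|---|---|---|
| 4.5 | 1.5 / 1 = 150% | 4.5 > 3.5: Yes | Yes | Yes |
| 3.5 | 0.5 / 1 = 50% | 3.5 > 3.5: No | 3.5 ≥ 3.5: Yes | No |

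The formula reproduces both printed answers. Only the label disagrees, and only on the second row.

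**Where label and formula differ when EDSS rose.** They differ only if later = T, which needs half the rise to be a multiple of 0.5, that is, a whole-point rise. From a pre-relapse EDSS of 3:

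- Rise 0.5: T = 3.25, not a possible score. The two always agree.
- Rise 1.0: T = 3.5. They differ at a later EDSS of 3.5.
- Rise 1.5: T = 3.75, not a possible score. The two always agree.
- Rise 2.0: T = 4.0. They differ at a later EDSS of 4.0.

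After a 1-point rise, +0.5 is the only score between full recovery (+0) and full retention (+1). Every partial recovery of that kind is therefore decided by the choice of inequality. One exception: from a pre-relapse EDSS of 0, a 1-point rise cannot tie, because Appendix 3 lists no level between 0.0 and 1.0.

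**Can a qualifying relapse leave EDSS unchanged?** Yes. In Appendix 3, EDSS 3.0 covers three or four functional systems at grade 2. A patient with three who gains a fourth by one listed scale going from 0 to 2 meets the FSS criterion and stays at 3.0. Likewise, EDSS 1.5 covers more than one system at grade 1, so moving from two to four such systems meets the two-scale criterion with no EDSS change.

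**What the rule then does.** With before = 3.0 and Chg-EDSS = 0, T = 3.0.

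- Later EDSS 3.0: 3.0 > 3.0 is false, so No, which is sensible.
- Later EDSS 3.5: Yes, although the percentage retained is undefined (0.5 / 0).

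Changing to ≥ with no other condition would make this worse: later 3.0 would also become Yes, since 3.0 ≥ 3.0.

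**A further route to the same gap.** Chg-EDSS starts from a scheduled visit, whereas relapse qualification says "Take the last EDSS/FSS score before each clinical relapse onset date", which is not limited to scheduled visits. Chg-EDSS can therefore be zero or negative even for a relapse that qualified on EDSS. With before = 3.0 and Chg-EDSS = −0.5, T = 2.75, and a patient simply back at 3.0 scores Yes. A condition that Chg-EDSS exceed 0 covers this too.

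**The case against.** The strongest reply is that the operative rule is not ambiguous. The formula and both example rows agree, the text promises the count that satisfies the formula, and the at-least wording appears only as a column heading in an illustration. The SAP does not say that the output tables will carry that heading. This stands, and it is why relabelling is the simplest repair; the contradiction within the section remains.

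A second reply is that a patient with no EDSS change at the relapse but a higher EDSS later does have more disability than before, so Yes is defensible in plain terms. That is fair as a description of the patient. It does not make the patient someone who retained half of a relapse-related rise.

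A third is that the section also summarises Chg-EDSS itself and the change to the next two scheduled assessments, so recovery can be seen without this dichotomy. That is true and limits the harm.

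A reader might infer two stronger claims that the documents do not support:

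- **That residual disability is understated.** Measured against its own formula, the count is not understated. Ties move patients out of Yes relative to the label, while relapses without an EDSS rise can move patients in, so the net direction is unknown. The separate yes/no item on residual disability in the same section is not said to be derived from this rule.
- **That relapses qualifying on FSS alone are misclassified as a group.** When Chg-EDSS is 0, only those with a later EDSS above the pre-relapse value are affected.

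**Conclusion.** The point holds as a small internal inconsistency plus a missing condition. After a whole-point rise, a patient who keeps exactly half is scored against the label. After a relapse with no EDSS change, a later EDSS above the pre-relapse value is scored as retention of a rise that did not occur.

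The size cannot be computed, because neither document gives the distribution of Chg-EDSS or the frequency of relapses without an EDSS rise. The conclusion rests on reading the inequality as strict, which the No in the second example row confirms independently, and on EDSS being scored as in Protocol Appendix 3.

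The measure is descriptive and exploratory. NEDA, 24-week confirmed disability progression and the annualized relapse rate do not use it. This is a worthwhile tidy-up and carries no weight for the trial's main conclusions.

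**What to change.** In SAP Section 4.4.3.6:

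1. Restrict the measure to protocol-defined relapses with Chg-EDSS above 0, and report relapses with zero or negative change separately.
2. Align label and rule. The simplest way is to keep the strict inequality and both example rows and relabel the column as more than 50%. The alternative is to use ≥ and change the second row to Yes, but only together with step 1, because on its own it would turn an unchanged EDSS into a Yes.

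The cost is a few words in the SAP and the matching programming specification. The downside is a slightly smaller set of relapses analysed for this measure, which the separate report of the remaining relapses makes visible.

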4.4.4 Sensitivity Analyses

All analyses (binary endpoint, Kaplan-Meier, Life Table) listed for the primary endpoint in section 4.4.1 will be repeated for a modified protocol defined event definition, where any clinical MS relapses will contribute for a more comprehensive analysis of relapses as collected during the study.

For the primary endpoint, several sensitivity analysis will be performed:

- This analysis will be repeated for ITT population without imputation of missing values i.e. patients who discontinued treatment prior week 96, regardless of the reason, will be excluded from the analysis as their disease activity status cannot be ascertained.
- The analysis will also be repeated on the NEDA defined from MRI at screening visit instead of using MRI at week 8 as baseline. For this analysis, the number of new or enlarged T2 hyperintense lesion at week 24 visit will corresponds to the sum of the number of new or enlarged T2 hyperintense lesions at week 8 and 24.
- The analysis will also be repeated on the NEDA defined from MRI at week 8 as baseline and from protocol defined relapses occurred from Week 8 (only protocol defined relapses with study day \geq 57 will be considered).
- The analysis will be performed regarding the MRIs are done after infusion at the same visit. We will manually remove the measurement on T1 Gd-enhancing lesions from these MRIs if zero T1 Gd-enhancing lesions from these MRIs are reported, because the premedication corticosteroids potentially has impact on this MRI (Barkhof F, [Neuroradiology](#). 1994) We will impute the presence of T1 Gd-enhanced lesion based on those MRIs if there is no T1 Gd-enhancing lesions identified. We consider this is a more conservative way than the primary analysis.

To summarize, five sensitivity analysis will be performed for NEDA:

Sensitivity Analysis	Modification
A	No imputation of missing values, regardless of the discontinuation reason.
B	MRI baseline at screening (week 0)
C	Use clinical relapse not the protocol defined relapse in the definition.
D	Rebaseline relapse (PDR) from week 8 (exclude the relapses occurring in the first 8 weeks)
E	If the number of T1 Gd-enhanced lesion from the MRI that done after infusion equals zero, it will be imputed

Modified protocol-defined event definition

The definition of a modified protocol-defined event of disease activity is the occurrence of at least one of the following individual events while on treatment with ocrelizumab:

- Any reported clinical MS relapse
- 24-weeks CDP based on increase in EDSS while on treatment with ocrelizumab
- A T1 Gd-enhanced lesion on MRI after week 8
- A new and/or enlarging T2 hyperintense lesion on MRI after week 8

Additionally, analyses of secondary efficacy endpoints from sections 4.4.2.5 and 4.4.2.6 will be repeated for all reported clinical MS relapses.

4.4.5 Subgroup Analyses

The primary and the secondary efficacy endpoints will be summarized by the following subgroups, provided that they include at least 50 patients:

- Last DMT prior to study enrolment
 - Interferons (Interferon β 1a, Interferon β 1b, Peg Interferon β 1a)
 - Glatiramer acetate
 - Teriflunomide
 - Fingolimod
 - Dimethyl fumarate
 - Natalizumab
- Age (\leq 40 years, $>$ 40 years)
- Disease severity at inclusion and in disease history:
 - EDSS at baseline ($<$ 2.5, \geq 2.5)
 - Number of relapses over the year prior to inclusion (\leq 1, $>$ 1)
 - MRI at Week 8: presence of T1 Gd+ (Yes/No)
 - time between the qualifying disease activity event (last relapse prior to study) while on last DMT and 1st dose of ocrelizumab ($<$ 6 months, \geq 6 months)

In addition, changes in EDSS and ARR at week 96 will be summarized separately for patients with and without NEDA upto week 96. ARR will be only be repeated on the patients without NEDA up to week 96.

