2.2.2 Secondary Efficacy Outcome Measures

The secondary efficacy endpoints are the following:

- Proportions of NEDA patients during the initial 24-week period and the initial 48-week period
- Time to first protocol-defined event of disease activity
- Change in EDSS from baseline to Week 96
- Proportion of patients who, over a 96-week period, have Confirmed Disability Improvement (CDI), CDP or stable disability (i.e. neither CDI nor CDP).
- Annualized rate of protocol-defined relapses at Week 96
- Time to onset of first protocol-defined relapse
- Time to onset of 24 weeks CDP
- Time to onset of first new and/or enlarging T2 lesion
- Total number of T1 Gd-enhanced lesions detected by brain MRI at Weeks 24, 48 and 96

- Change in total T2 lesion volume detected by brain MRI from Week 8 to Week 96
- Volume and number of new and/or enlarging T2 hyperintense lesions from Week 8 to Weeks 24, 48 and 96
- Change in T1 hypointense lesion volume from Week 8 to Weeks 48 and 96
- Percentage change in brain volume from Week 8 measured at Weeks 24, 48 and 96
- Percentage change in white matter volume from Week 8 measured at Weeks 24, 48 and 96
- Percentage change in cortical grey matter volume from Week 8 measured at Weeks 24, 48 and 96
- Change from baseline in cognitive performance at Week 48 and Week 96 as measured by the components of the Brief International Cognitive Assessment for Multiple Sclerosis (BICAMS)

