4.4.2.2 Time to first protocol-defined event of disease activity

The analyses will include patients in the mITT population.

Patients with early study discontinuation before any disease activity event will be censored at the withdraw date, which is defined in Section 4.6.1. It will be imputed as having an event if discontinuation reason is lack of efficacy or death.

1) Kaplan-Meier analysis of time to first protocol-defined event (refer to section 4.4.1), with estimates (Greenwood 95% confidence intervals using a log-log transformation) of proportion of patients with NEDA determined at week 96 and week 104 (or time of the last event/censoring if that is before week 104). Kaplan-Meier plots will be produced up to the last available time of censoring or event.

2) Life-table analysis will be used to estimate the survival probability of time to first protocol-defined event, with estimates and Greenwood 95% confidence intervals using a log-log transformation by using time intervals which correspond to planned MRI assessments (weeks 24, 48 and 96). Thus, exact time of protocol-defined relapses and 24-weeks CDP will fall within MRI time intervals such as [week 8-week 24), [week 24-week 48), [week48-week96) and [week 96, -end of study]. Life-table plots will be produced.

Sample SAS code can be found below (SAS code is regarded as “draft” until fully validated at the analysis stage):

a) Binary method

```
ods output binomial=dataset BinomialTest=tpvalue;  
proc freq data=event ate;  
    tables eventyn / binomial (level='1') alpha=0.05;  
run;
```

b) Kaplan-Meier method

```
proc lifetest data=dataset method=km conftype=loglog outsurv=surv plots=none notable
STDERR;
time aval*eventyn(1);
run;
```

c) Life -Table method

```
proc lifetest data=dataset method=life conftype=loglog intervals=24 48 96 outsurv=surv
plots=none STDERR;
time aval*eventyn(1);
run;
```

4.4.2.3 Change in EDSS from baseline to week 96

EDSS (actual value, change, percentage change from baseline) will be summarized at each visit (up to week 96) for the ITT population. The change in the eight function scores from baseline up to week 96 will also be summarized for the ITT population.

Additionally, summary statistics will also be presented at week 96 for the following categories of change in EDSS:

- worsened (>0.5),
- stable ($-0.5, 0, 0.5$)
- improved (<-0.5)

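### Change in EDSS is tabulated by the same baseline EDSS it is measured from, so regression to the mean adds a spurious contrast between the two subgroups

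*SAP*

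**What the plan says.** - SAP 4.4.5: "The primary and the secondary efficacy endpoints will be summarized by the following subgroups, provided that they include at least 50 patients". The list includes "EDSS at baseline", split into below 2.5 and 2.5 or above. Protocol 6.6 prespecifies the same cut.
- SAP 2.2.2 lists "Change in EDSS from baseline to Week 96" as a secondary endpoint.
- SAP 4.4.2.3: "EDSS (actual value, change, percentage change from baseline) will be summarized at each visit (up to week 96) for the ITT population". It adds that "summary statistics will also be presented at week 96 for the following categories of change in EDSS": worsened (above 0.5), stable (-0.5 to 0.5) and improved (below -0.5). An MMRM of the change has baseline EDSS as a continuous covariate.
- SAP 4.4.1, in the CDP definition: "Because of the variability of EDSS, a single measurement at the baseline visit might not provide a sufficiently reliable baseline EDSS". For CDP it therefore averages the screening and baseline scores, and 4.4.2.4 carries the CDP derivation over to CDI. The SAP does not say whether the average also applies to change in EDSS or to the subgroup cut.
- Protocol section 6 describes a single-arm, non-comparative study with exploratory, mainly descriptive analysis.

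Neither document exempts change in EDSS from this subgroup or mentions regression to the mean.

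**The concern.** A patient can fall below 2.5 because the true EDSS is low or because that day's rating happened to be low. The chance part does not recur at Week 96, so the low group drifts up with no real change. The high group drifts down for the same reason. In a randomised trial both arms would carry the same drift within a stratum and it would cancel. Here nothing cancels it.

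At stake is the reading of one subgroup table. Part of any difference in EDSS change between less and more disabled patients would come from how the table is built. Once the table stands alone, that part cannot be separated from a real difference.

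**Working it through.** **Plan figures.** The documents give no figure for EDSS change by baseline EDSS. Their design figure for NEDA reproduces (225/750 gives a Clopper-Pearson interval of 26.74% to 33.42%) but has no bearing here.

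**Inputs from the documents.** Cut at 2.5 (SAP 4.4.5); screening EDSS 0.0 to 4.0 for entry (Protocol 4.1.1); EDSS scheduled at screening (weeks -4 to -1), baseline and Week 96 (Protocol Appendix 1); category limits (SAP 4.4.2.3).

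**Assumed, because the documents are silent.** No true change; true EDSS mean 2.1, SD 0.9 to 1.1; rating error independent between visits, SD 0.2 to 0.5. Reliability is true variance over total variance: 0.81/(0.81 + 0.25) = 0.76 at the noisiest setting and 1.21/(1.21 + 0.04) = 0.97 at the cleanest.

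**Direction, in closed form.** For an untruncated normal score with reliability R, total SD s and c = (2.5 - mean)/s, the expected change with no true change is

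- low group: +(1 - R) × s × φ(c)/Φ(c)
- high group: -(1 - R) × s × φ(c)/(1 - Φ(c))

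Example: mean 2.0, s = 1.0, R = 0.8, so c = 0.5, φ = 0.352, Φ = 0.691. Low: 0.2 × 0.352/0.691 = +0.10. High: -0.2 × 0.352/0.309 = -0.23. The signs hold for any R below 1, and the shift is zero at R = 1.

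**Size, by simulation.** Scores were rounded to EDSS steps, entry required a screening score of 4.0 or less, and change is Week 96 minus the reference score.

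| Classified by | Change from | Error SD | Low group | High group | Contrast |
|---|---|---|---|---|---|
| baseline | baseline | 0.3 to 0.5 | +0.07 to +0.19 | -0.09 to -0.25 | 0.16 to 0.43 |
| baseline | baseline | 0.2 | | | 0.09 to 0.11 |
| average | average | 0.3 to 0.5 | | | 0.08 to 0.22 |
| screening | baseline | 0.3 to 0.5 | 0.00 | 0.00 | 0.00 |

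For the first row, worsened is about 8 to 22% in the low group against 3 to 8% in the high group. Improved is about 5 to 11% against 7 to 23%; at the smallest error in that range the improved shares are nearly equal. Overall mean change stays at about 0, so the artefact appears only once the table is split.

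**Other assumptions.** With mean 2.0 to 2.5, total SD 1.0 to 1.3 and reliability 0.7 to 0.9, the contrast is 0.20 to 0.69, against a standard error of about 0.04 to 0.07 for 750 patients. That run allowed a 0.5 step, which the scale in Protocol Appendix 3 lacks, so it supports the direction and order of size only.

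**Dependent errors.** If screening and baseline errors are correlated, classifying by screening does not remove the whole contrast. At correlation 0.5 it leaves 0.06 to 0.19 (about 40%); at 0.8 it leaves 0.10 to 0.30 (about 60 to 70%).

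**The case against.** **The study is exploratory.** No test, interaction or decision rests on this table. That stands, and it limits the weight of the point. It does not make the table neutral: a descriptive table with no comparator tends to be read at face value.

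**The MMRM adjusts for baseline EDSS.** That is the overall model. Fitted within a subgroup, it gives means at that subgroup's own baseline mean, so the shift stays. SAP 4.4.5 in any case speaks only of summaries.

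**The size is assumed.** It stands. It falls to about 0.1 at error SD 0.2, and roughly halves if the averaged baseline is meant here. All the simulated mean shifts lie inside the SAP's stable band; only the category shares cross it.

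**A reader might infer more.** One could conclude that the table will show worsening in the low group and improvement in the high group, and so credit ocrelizumab with benefit only in more disabled patients. The documents do not support that forecast. Observed means will also contain true change, treatment effect and recovery from recent relapses, so the final signs are open.

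**The remedy is imperfect.** It stands. The two visits are 1 to 4 weeks apart and a clinical relapse can qualify a patient for entry, so a deviation lasting across both visits is plausible. Re-cutting the subgroup for every endpoint would also depart from Protocol 6.6 to repair one table.

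**Conclusion.** The concern holds in limited form. For change in EDSS and its three categories, SAP 4.4.5 classifies patients by the score that also serves as the reference for change. With no control arm, this adds an upward shift below 2.5 and a downward shift at 2.5 or above.

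The direction follows from the variability that the SAP itself concedes. The size, about 0.09 to 0.43 points with a single baseline score, rests wholly on the assumed mean, SD and independent error.

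A reader might also infer that the main results are biased. They are not: the overall EDSS change and the whole-population NEDA proportion do not depend on this split. CDP and CDI cut the same way would lean in the same direction, but no size was worked out for them and they are outside this point. This is a cheap improvement to one planned table.

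**What to change.** Keep the protocol's baseline-EDSS subgroup for all other endpoints. Add to SAP 4.4.5 that, for change in EDSS and its worsened, stable and improved categories only:

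- patients are classified by the screening EDSS (below 2.5, 2.5 or above);
- change is measured from the baseline-visit EDSS taken before first dose;
- patients missing either score are left out of this table, and their number is reported.

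This table can replace the planned one or stand beside it; in the second case a footnote should name regression to the mean. SAP 4.4.2.3 should also state which baseline it uses.

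The cost is a few lines of SAP text and a different input variable, with no new data. The drawbacks are that some patients near 2.5 will be classed differently from the baseline table in SAP 4.3, and that the reference score may differ from that of the overall analysis if 4.4.2.3 turns out to mean the average. Fluctuation that lasts across both visits leaves part of the artefact, so the footnote is useful in either case.
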